for measurements of forearm blood flow using venous occlusion plethysmography c. A physician trained in brachial artery catheterization in the Human Cardiovascular Research Lab will then perform brachial artery catheterization with 27 G needle and undergo incremental infusions of saline, acetylcholine, acetylcholine + vitamin C (ascorbic acid), and sodium nitroprusside + vitamin C (see Expermental Procedures for details)

- d. Subject will be escorted to Dept of Ophthalmology in Pomerantz Bldg and have picture of retinal performed (scan takes  $\sim$ 10 min)
- e. Subject will be given snack or lunch in CRU.
- f. Subjects will be randomized in a 2:1 scheme to Salsalate or placebo
- g. Nurse will dispense 35 day supply (210 tablets) of Salsalate (dose 3000 mg/day = 500 mg tablets x  $6/\text{day} \times 35 \text{ days} = 210 \text{ tablets}$ ) or placebo
- h. Subject will take first dose of Salsalate (500 mg x 3 pills) or placebo at CRU and 2nd dose (1500 mg) at home in evening- this is Day 0

Visit 5 (45 min) ~Day 14: Subject will return to CRU for venous blood sample to measure serum salicylate (4.5 ml x 2 PST tubes: total 9 ml or ~0.5 tablespoons), Blood pressure, HR and survey of any side effects. If any side-effects/symptoms present, nurse coordinator will follow instructions as outlined in section VIII.2 "Plan for Managing Risks". Subject will receive 3-day food record booklet from CRU bionutritionist

Days 25: Coordinator or research staff will call subject in the evening to remind subject to start 3-day dietary record on days 26, 27, 28.

Visit 6 (5 hours) Betwee Day 26-34: Post-experimental visit #1 (FMD, PWV and Retina)

- a. Subject will take morning dose of Salsalate/placebo and return to CRU between Day 26 -35 for venous blood sample to measure serum salicylate, blood pressure, HR; and survey of any side effects
- b. All vascular measurements of Visit 3 will be repeated
- c. Middle cerebral artery blood flow velocity using transcranial dopper during the following protocol to measure cerebral vasoreactivity to hypercapnia:
- -After 3 min of normal breathing, subjects will perform 2, 30 second breathholds sparated by 3 min.
- -Next, After 3 min of room air breathing, 3 min of breathin 2%CO2, 3 min of breathing 4%CO2 (balanced with 21%O2 and N) will be performed followed by 3 min of room air

breathing.

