determine that a neurogram represents sympathetic activity to muscle or skin: We have used this technique safely in over 2000 studies since February 1984 and it is well tolerated and reproducible. The mental stress test is a non-baroreflex mediated sympathoexcitatory stimulus used to test sympathetic responsiveness. This test requires that each subject to subtract continuously the number 7 from a 3-digit number as quickly and as accurately as possible for 3 minutes. During the test, the participants are intentionally frustrated by being asked to calculate faster and by being corrected in case of wrong answers. This stimulus has little effect on muscle SNA and increases forearm blood flow.

c) 24-hour ambulatory blood pressure variability and baroreflex sensitivity. Twenty-four hour systolic blood pressure will be recorded using standard ambulatory blood pressure assessment (90207-IQ, Spacelabs Healthcare, Inc)and 24 hour blood pressure variability determined from the standard deviation of systolic and mean blood pressure recordings. Baroreflex sensitivity will be determined by recording blood pressure and heart rate continuously for 15 minutes during visit 3 and 6 using via beat-to-to beat finger blood pressure (Finometer MIDI, Finopress Medical Systems) and calculated using the sequence technique.

Microneurography training controls:

We will recruit 20 additional healthy control volunteers who will have microneurography performed on them by [name]. The training will be provided by [name] and [name], both of whom are highly trained in the technique and will provide close oversight in the training. The 20 volunteers will sign and separate consent form (see attached) and will be compensated \$25.

- VII.E.7 Will you attempt to recontact subjects who are lost to follow-up?

  No followup is not required in this study
- VII.E.9 Will subjects be provided any compensation for participating in this study?

  Yes
  - VII.E.10 Cash

No

VII.E.11 Gift Card

No

VII.E.12 Check

Yes

VII.E.13 Who will be providing the research compensation check to the subject?

Accounting Services directly via the e-Voucher system

VII.E.16 Other

No

- VII.E.19 Describe the compensation plan including
  - · Compensation amount and type per visit
  - Total compensation
  - Pro-rating for early withdrawal from study

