### Plan for Monitoring for Risks:

During the study if the subject experiences any mild but tolerable expected side effects such as tinnitus, dizziness, nausea, headache, they will be asked to keep a log of these including the date, the duration, and the severity by rating on a scale of 1 (mild) to 10 (severe/intolerable). If the subject feels the side effects are uncomfortable or intolerable, then they will be instructed to call in to the Research Nurse during business hours. If after business hours, weekends, or holiday, the subject will be instructed to call in the UIHC access number and ask for [name] to be paged. The Research Nurse or [name] (although he will be blinded) will instruct the subject to skip the next dose and if the symptoms/side effects have resolved at time of next dose (in 12 hours), they will be instructed to take the next dose at 500 mg less and continue at that dose. [name] will call/page [name] for

consultation if necessary and [name] will serve as back up if [name] is out of town or unavailable. If [name] is out of town or unavailable then [name], MD will be available to consult. If symptoms do not resolve or worsen at time of next scheduled dose, the subject will be instructed to not take that dose, and to come to the CRU to have a blood sample to assess serum salicylate concentrations. If side effects that are life threatening, the subject will be instructed to call 911. If serum salicylate concentrations are not in the toxic range (<30 mg/dl), the subject will be will be re-assessed in 12 hours to confirm that salicylate concentrations are decreasing and symptoms resolved. If symptoms resolve, the subject can take next am or pm dose at 500 mg lower or be withdrawn from the study as recommended by [name].

If blood plasma salicylate concentrations are in the toxic range (>30 mg/dl), the subject will be withdrawn from the study and [name] and [name] notified. Serum electrolytes (including anion gap), urinalysis and respirations may be obtained in the case of suspected metabolic acidosis due to Salsalate toxicity. If metabolic acidosis is suspected, then [name] will be notified and determine appropriate medical management in the CRU or referral to the UIHC Emergency Department.

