### XI. Data Analysis

### XI.1 Describe the analysis methods you will use, including, if applicable, the variables you will analyze

Statistical analyses. To determine if differences in outcomes are present at baseline between obese pre-diabetic vs. non-pre-diabetic groups, an independent two-sample t-test will be performed. To determine if baseline (pre-intervention) differences exist between salsalate and placebo prediabetic groups after randomization, independent two-sample t-tests will be performed. To test the main hypotheses, a repeated measures ANOVA will be performed in which treatment (salsalate vs. placebo) is the between-subjects factor, and time (pre- vs. post-intervention outcomes) is the within-subjects factor for the primary dependent variables. The critical test for the dependent variable will be the interaction between the within-subjects and betweensubjects factors. Tests for mean contrasts will be used to compare variables of interest pre vs. post Salsalate or placebo. Based on a previous study, we expect small reductions in fasting glucose, triglycerides, LDL cholesterol and possibly systolic blood pressure after Salsalate treatment. Covariates (e.g., variables that change after Salsalate) will be included into the mixed model. Bivariate pearson correlation analysis will be performed on the change in each dependent variable and aforementioned selected covariates after Salsalate.

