### XI.2 Provide the rationale or power analysis to support the number of subjects proposed to complete this study.

Sample size calculations. Sample sizes were calculated based on 80% power at an alpha level of 0.05. Estimated effect sizes for Aim 1 were used for final sample size calculation for obese prediabetic subjects because carotid-femoral PWV is the primary outcome and has the smallest effect size (d) in pilot data of 4 days before vs. after Salsalate. A sample size of 16 subjects per group was determined based on the d of 1.06, based on mean difference in carotid-femoral PWV (-1.0  $\pm$  1.0 m/sec) after Salsalate vs. Placebo.

With a conservative estimated attrition rate of 15-20% and the 2:1 randomization, a total of 20 subjects will be assigned to the Salsalate group, and 10 subjects to the placebo group was determined to be required for the study (total sample size=30). A

sample size of 12 for Aim 2 (FMD) was determined from d of 1.2 for a mean difference in FMD of  $\pm$  2.2 after 4 days Salsalate vs placebo based on previously published work by the PI (19). Because the effect sizes for Aim 1 and 2 are based on preliminary data of 4 days of Salsalate treatment and our proposed study is 4 weeks, we predict that the actual effect sizes will be slight higher because of the longer duration of treatment. Therefore, the proposed study will help determine actual effect sizes for chronic Salsalate therapy for a future larger randomized clinical trial.

A total of 10 obese non-prediabetic control subjects will be recruited to established differences in main outcomes at baseline but will NOT undergo randomization or salsalate/placebo treatment period.

Therefore, total sample size to be enrolled is 40.

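### Subjects withdrawn for side effects leave the study before the only post-treatment PWV, so the pilot's effect size could describe mainly those who stayed on tablets

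*Combined protocol and SAP*

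**What the plan says.** VIII.2 (Plan for Monitoring for Risks) has two routes by which side effects or toxicity end participation.

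- **Discretionary.** After a skipped dose, a reduced dose and, if needed, a salicylate check: "If symptoms resolve, the subject can take next am or pm dose at 500 mg lower or be withdrawn from the study".
- **Mandatory.** "If blood plasma salicylate concentrations are in the toxic range (>30 mg/dl), the subject will be withdrawn from the study".

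Both routes lead out of the study. Neither separates stopping tablets from ending measurement.

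In VII.E.6, Visit 6 opens with "Subject will take morning dose of Salsalate/placebo and return to CRU between Day 26 -35" and continues with "All vascular measurements of Visit 3 will be repeated". Visit 3 is where baseline PWV is taken, so Visit 6 supplies the only post-treatment PWV. Baroreflex sensitivity follows the same two visits: "Baroreflex sensitivity will be determined by recording blood pressure and heart rate continuously for 15 minutes during visit 3 and 6". The written visit list contains no early-termination or post-withdrawal outcome visit, and VII.E.7, on recontacting subjects lost to follow-up, answers that follow-up is not required.

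On analysis, XI.1 states: "The critical test for the dependent variable will be the interaction between the within-subjects" and between-subjects factors. It names no analysis set and no rule for missing outcomes. XI.2 begins its allowance for losses "With a conservative estimated attrition rate of 15-20"% overall, not split by arm, and gives the purpose of the estimate: "the proposed study will help determine actual effect sizes for chronic Salsalate therapy for a future larger randomized clinical trial".

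**The concern.** A pre-post comparison needs a post value. If a subject who stops because of side effects also leaves the study, that value is never collected and cannot be recovered later. The pilot then estimates the effect mainly in subjects who tolerated the drug. A larger trial analysed as randomised would include those who stopped, so a planning value taken from tolerators alone could leave it short of subjects.

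There is some reason to expect unequal losses. Other salicylates and aspirin are excluded or washed out (VI.13), so in practice the 30 mg/dl rule can act only on the salsalate arm, and the side effects that trigger the discretionary route are those attributed to salsalate in VIII.1. If losses are unequal and related to response, the randomised comparison is also exposed to selection bias.

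**Working it through.** **1. The plan's own figure.** XI.2 gives d = 1.06, 80% power, alpha 0.05 and 16 per group. A two-sided two-sample t-test (sidedness is not stated, two-sided assumed) needs 15 per arm, and the normal approximation gives 14. At 16 per arm, power is 83%. The stated figure is reproduced to within two subjects. Allowing for 20% attrition, 16/0.80 = 20, which is the salsalate arm of the 20:10 design.

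**2. How many might stop.** VIII.1 gives a wide spread:

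- One withdrawal is reported in the 108-patient randomised trial of placebo or 3.0-4.0 g/day for 14 weeks. Three dose reductions were followed by completion. Total withdrawals are not stated.
- None is reported among 17 diabetic patients at 3-4 g/day for 4 weeks.
- 3/20 = 15% at 4 g/day for 4 weeks (rash).
- 2/17 = 11.8% at 4.5 g/day for 4 days.
- 234/782 = 29.9% at about 3 g/day, in arthritis patients.

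I use 5% (one of 20, an assumed low case), 12% (2/17) and 20% (the top of the planned attrition).

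**3. Size of the shift.** Assumptions: the effect is 1.06 SD in stayers and zero at Visit 6 in stoppers; the within-group SD is 1; p is the proportion of the salsalate arm that stops.

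- Difference as randomised = 1.06 × (1 − p); shift = 1.06 × p.
- Salsalate-arm variance = 1 + 1.06² × p(1 − p).
- Pooled 1:1 SD = √[(that variance + 1)/2].
- Standard error of the pilot's difference = √(1/20 + 1/10) = 0.387 SD.

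For p = 0.20: difference 1.06 × 0.80 = 0.848; shift 0.212; variance 1 + 1.1236 × 0.16 = 1.180; pooled SD 1.044; standardised d = 0.848/1.044 = 0.812; n = 25 per arm.

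| Stopping | Shift (SD) | Shift / pilot SE | Standardised d | n per arm, later 1:1 trial | n per arm if half the effect remains |
|---|---|---|---|---|---|
| 0% | 0 | 0 | 1.06 | 15 | 15 |
| 5% | 0.05 | 0.14 | 0.99 | 17 | 16 |
| 12% | 0.12 | 0.32 | 0.91 | 20-21 | 18 |
| 20% | 0.21 | 0.55 | 0.81 | 25 | 19 |

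The last column replaces the shift by 0.53 × p and the variance term by 0.53² × p(1 − p). At 12%, 20 per arm lies on the 80% boundary, hence the range.

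**4. What measuring stoppers does to the pilot's power.** If 4 of 20 stop with no residual effect, as-assigned power at 20 v 10 is about 51%, against 71% for the on-treatment comparison (16 v 10).

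**The case against.** The strongest case against has four parts.

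- **Few may stop.** The most comparable evidence, the randomised trial that includes this dose and runs longer, reports one withdrawal, in a patient with tinnitus at baseline. One small study at 3.0 g/day for 2 weeks saw no side effects. VIII.2 also offers a skipped and then a reduced dose before withdrawal. This stands, and it is why the low case belongs in the table.
- **The schedule may be incomplete here.** VII.E.6 refers to a Table 1 attachment summarising the visits, which is not available in the text reviewed. Visit 6 also does not expressly bar subjects who have stopped. So the absence of a post-withdrawal visit is judged from the written visit text only.
- **XI.1 mentions a mixed model.** Such a model could retain a withdrawn subject's baseline, but a baseline alone adds little about the treatment-by-time interaction. The wording arises in connection with covariates, and no missing-data assumption is stated.
- **It is a pilot.** VII.E.2 says the 2:1 allocation was chosen to determine effect sizes in the salsalate group, so an on-treatment estimate may be what the investigators want. That is a fair choice, but XI.1 does not state it.

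A reader might infer from the arthritis series that about 30% of the salsalate arm will be lost. The documents do not support carrying that figure over: this trial excludes ulcer, dyspepsia, severe reflux disease and rheumatoid arthritis (VI.13), and its phone screen asks about tinnitus (VII.D.20). A reader might also infer that the 30 mg/dl rule will remove many salsalate subjects. The levels cited in VIII.1 make that unlikely: 28.4 and 19.0 mg/dl at 4.5 g/day, and 5.4 mg/dl at 3.0 g/day.

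**Conclusion.** The point holds in a limited form. Followed as written, the plan loses the primary outcome in any subject withdrawn before Visit 6, and nothing in XI.1 says how such subjects enter the analysis. The consequence is a small to modest distortion of the planning value: 0.05 to 0.21 SD, or 0.14 to 0.55 of the pilot's own standard error, at 5-20% stopping. That rests on no residual effect in stoppers, and half of it would remain if half the effect persisted.

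Two stronger conclusions are not supported. Greater loss on salsalate is plausible but not shown, since no placebo discontinuation rate is given and the placebo comparison in VIII.1 says only that mild gastrointestinal symptoms were slightly more common on salsalate. Nor can it be said that the pilot will overstate the effect in those it measures, because the direction of any selection bias cannot be settled from the documents. The change is worth making because it is cheap and the data cannot be recovered afterwards. The gap does not invalidate the trial.

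**What to change.** Leave the dosing, tablet-stopping and unblinding rules as they are.

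1. **VIII.2 and VII.E.6:** state that stopping tablets does not by itself end outcome measurement. Invite every randomised subject who stops, if willing and medically able, to the already planned Visit 6 for the non-invasive outcomes: PWV, flow-mediated dilation, blood pressure and finger-pressure baroreflex sensitivity. Keep the assessors blinded. VII.E.1.c allows a subject withdrawn for an adverse event to be told the assignment, so ask such subjects not to disclose it.
2. **XI.1:** report the as-assigned estimate in all randomised subjects with outcomes alongside the on-treatment estimate, and name in advance which is primary. That choice is the investigators'.
3. **Reporting:** give attrition and its reasons by arm. VIII.4 already collects them overall.

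The cost is short text in three sections. At 5-20% stopping, one to four salsalate subjects would keep a Visit 6 paid at $75 (VII.E.19), so 1 × $75 = $75 to 4 × $75 = $300, within planned payments, plus staff and research-unit time within a visit already planned. Off-drug values dilute the as-assigned estimate, which is why both estimates are reported. Invasive outcomes (microneurography and forearm blood flow) would still be missing in those who stop.

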#### **DESCRIBE:**

- What subjects will be asked to do/what happens in the study (in sequential order)
- The time period over which procedures will occur
- The time commitment for the subject for individual visits/procedures
- Long-term followup and how it occurs

Experimental design. A total of 30 obese (defined as body mass index >30 kg/m2) adults age 18-49 years with prediabetes will be enrolled and randomized to 4-5 weeks of Salsalate or placebo in a randomized (2:1), double-blind, placebo controlled, parallel study design. Subjects will orally ingest 3000 mg/day (1500 mg in a.m. and 1500mg in the p.m.) of Salsalate (n=20) or placebo (n=10) for 28-35 days. A total of n=10 obese NON-prediabetic CONTROL subjects will be enrolled to establish prediabetes-related differences in obese adults primary outcomes at baseline. Therefore, a total of 40 subjects will be enrolled. The non-prediabetic control subjects will undergo screening (Visits 1 and 2) and baseline experimental testing (Visits 3, 4) but will NOT undergo the Salsalate/placebo intervention or visits 5, 6 or 7. Prediabetes will be defined as fasting (at leaset 8 hour fast) blood glucose between 100-126 mg/dl, a fasting blood glucose of 140-199 mg/dl at 120 min during an oral glucose tolerance test, or HbA1C between 6.0 – 6.5%.

Order of visits. Subjects will undergo experimental testing at baseline and again after the 4-5 weeks of Salsalate or placebo. Subjects will be studied between 7:00 and 10:00 am in the Clinical Research Unit (CRU) in the Institute for Clinical and Translational Science (ICTS) at the University of Iowa following an 8 hour overnight fast. The order of visits are as follows and will occur over a period of 7-8 weeks (see TABLE 1 attachment for summary of visits):

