- b. Subjects on vasoactive medications will be asked to hold medication on the morning of experimental visits but to bring the medications with them to be taken after the visit.
- c. Return 3-day dietary recall
- d. IV catheter, endothelial cell collection and blood sample: Subject will lie supine and research nurse will insert venous 18 G catheter into antecubital vein.
- e. Research staff or physician will perform J wire endothelial cell collection (3 wires) via 18 G catheter.
- f. After 20 min, nurse practitioner will then obtain blood samples thru catheter:
- Lipid panel, insulin, hs-CRP, salicylate, creatinine, AST/ALT (4.5 ml blood- light green PST tube)
- Catecholamines (8 ml blood- 2 x 4 ml Na+ Hep green top tubes)
- HbA1c (4.5 ml blood- 1 x 4.5 ml lavender top tubes)
- Extra blood collected for specialized labs performed in PIs lab:

Serum: 17 ml blood-  $2 \times 8.5$  red/gray top SST tube) for interleukin-6, tumor necrosis factor-alpha.

Whole blood (17 ml blood-  $3 \times 8.5$  ml Citrate PPT tube) for mononuclear cell DNA isolation.

- f. After 15 min supine rest the following non-invasive vascular measurments are obtained by the PI and his research staff:
- 1) Radial, brachial, carotid and femoral waveforms non-invasively for PWV assessment
- 2) Carotid artery compliance using ultrasonography
- 4) Brachial artery flow-mediated dilation (FMD) with ultrasound
- 5) Brachial artery dilation after 0.3 mg sublingual nitroglycerin with ultrasound
- g. Subject escorted to the CRU Human Cardiovascular Research Lab and a physician or research staff trained in microneurography will insert needle into peroneal nerve for measurement of muscle sympathetic nerve activity
- h. Subject will meet with bionutritionist and review 3-day food record with subject
- i. Subject receives meal/snack from CRU bionutrition and then can leave
- \*\*TOTAL blood collected for Visit 3= 68 ml (~4.5 tablespoons)

Visit 4 (4.5 hours): 2nd Baseline experimental visit (Forearm Blood Flow and Microneurography)

- a. Subject comes to the CRU Human Cardiovascular Research Lab in the CRU between 7-10am after 8 hour overnight fast
- b. Subject will be instrumented with upper arm venous occlusion cuffs and wrist cuffs

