Scheduled safety visit. Subjects will come in at 2 weeks for Visit 5 (approximately Day 14 depending on scheduling) and to have serum salicylate concentrations measured and to confirm no toxicity. The Research Coordinator/Nurse or research staff will review their 2 week side effect log (see attached survey) and survey subjects for any symptoms/side effects and. Subjects will also have serum salicylate concentrations measured at experimental visits 6 and 7.

- VIII.3 Does this study have a plan to have an individual or committee review combined data from all subjects on a periodic basis (such as summary or aggregate safety and/or efficacy data)?

  Yes
  - VIII.4 Describe the plan to review combined data from all subjects, such as summary or aggregate safety and/or efficacy data. Include the following:
    - Describe what data will be summarized and reviewed
    - Describe how frequently data will be reviewed.

The Data Safety Monitoring Plan will consist of a bi-annual independent review of the protocol by [name], Department of Internal Medicine, Division of Nephrology. The PI will provide a bi-annual report to the [name] summarizing the following:

- a) Data on progress of the protocol including subject recruitment, attrition, and minority involvement. Reasons for attrition or other recruiting issues
- b) Data on safety of research participants including unblinded data of serum salicylate, creatinine, ALT/AST concentrations at baseline and from safety visits, data on reasons for any dosing reductions in Salsalate that occurred, and data collected from evening telephone questionnaires for subject symptoms;
- c) Data on compliance in reporting of any adverse events
- d) Data on protocol compliance and any amendments to the protocol
- e) Data on any safety issues that occurred during the 6 month period.
- f) He will confirm that any action that results in the temporary or permanent suspension of the protocol is reported to all the appropriate monitoring bodies such as the CRR protocol committee, IRB, FDA, NIH, or other sponsor, etc.

Every 12 months, the PI will summarize outcome data and provide to [name] for review of the efficacy of treatment intervention on primary outcomes

VIII.5 Will overall safety monitoring be performed by individual(s)/committee at The University of Iowa. (NOTE: If this study involves more than

minimal risk, in most cases these should be individuals who are not members of the study research team.)?

Yes

VIII.6 List names:

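### The PI supplies reports containing unblinded serum salicylate while the PI and staff measure the primary outcome, and the visible text states no safeguard between the two

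*Combined protocol and SAP*

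**What the plan says.** Section VII.E.6 (Experimental design) describes a "double-blind, placebo controlled, parallel study design".

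The monitoring plan in VIII.4 states: "The PI will provide a bi-annual report to the" independent reviewer. Item b of that report lists "Data on safety of research participants including unblinded data of serum salicylate, creatinine, ALT/AST concentrations at baseline and from safety visits". Item e refers to a six-month period, so bi-annual means twice a year. The same section adds a yearly task: "Every 12 months, the PI will summarize outcome data and provide to" the reviewer, so that efficacy on the primary outcomes can be assessed. The form's own prompt describes the material as combined data, "such as summary or aggregate safety and/or efficacy data".

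On measurement, VII.E.6 (Visit 3) says "the following non-invasive vascular measurments are obtained by the PI and his research staff"; the list includes PWV and FMD. For Visit 6 it says "All vascular measurements of Visit 3 will be repeated", with no other operator named. XI.2 makes carotid-femoral PWV the primary outcome.

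Two visible statements concern the blinding of particular study personnel. The endothelial-cell technician is blinded to subject identity (VII.E.6, Experimental Methods for Visit 3). One person who takes side-effect calls, whose name is removed, is said to be blinded (VIII.2).

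**The concern.** Serum salicylate is close to a marker of treatment in this trial. Other salicylates are excluded or washed out (VI.13, VII.B.3), so a clearly raised value after randomization points to the active arm. Someone who assembles a subject-level list of these values can largely infer assignments. Someone who assembles a table by arm needs the allocation itself. VIII.4 gives the task of supplying the report to the PI, and the PI belongs to the group that obtains the primary outcome.

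PWV and FMD depend on how the operator captures the signal and, for FMD, on later reading of stored images. Timing to the ECG R wave, a clamped ultrasound probe and analysis software (VII.E.6) limit operator influence, but they do not replace masking of those who capture and read the signals. XI.2 intends the trial to supply effect sizes for a larger one, so a doubt about the blind would carry into that planning. The placebo arm has only 10 subjects.

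**Working it through.** The plan gives no figure to reproduce on this point. The check is of who handles what, followed by an estimate of scale.

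**Roles side by side**

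- Report supplier: the PI, six-monthly and yearly (VIII.4).
- Report content: salicylate data expressly called unblinded (VIII.4, item b).
- PWV and FMD operators: the PI and research staff (VII.E.6, Visit 3), repeated at Visit 6. The text does not say which of them acquires each measure.
- PWV and FMD readers: none named as masked. FMD images are stored and analysed later.
- Separate compiler of the report: none named in the visible text.
- Route to salicylate values outside the report: salicylate is measured at Visits 5, 6 and 7 (VIII.2). Study data go into REDCap, and some into shared Excel and SPSS files, all open to research staff on the approved study (X.4).

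**Does salicylate reveal the arm?** Studies cited in VIII.1 report mean levels of 5.4 mg/dl at 3.0 g/day and 17.1 mg/dl at 4 g/day. Placebo levels near zero are an assumption. Under it, individual values would largely separate the arms.

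**Expected share with a Day 14 value in a report before Visit 6**

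Assumptions: values listed by subject, even accrual, reports exactly six months apart, and Day 14 results available at once.

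- Report interval: 365.25 / 2 = 182.6 days.
- Day 14 to Visit 6 (Day 26–34 in the visit heading): 26 − 14 = 12 days; 34 − 14 = 20 days.
- Share: 12 / 182.6 = 6.6%; 20 / 182.6 = 11.0%.
- Of 30 enrolled: 30 × 6.57% = 1.97; 30 × 10.95% = 3.29.
- After the 15–20% attrition in XI.2: 30 × 0.80 = 24 and 30 × 0.85 = 25.5 remain; 24 × 6.57% = 1.58; 25.5 × 10.95% = 2.79.
- Item a of Visit 6 allows Day 35: 21 / 182.6 = 11.5%, or 3.45 of 30.

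**What this leaves out.** It is an expected count for one route. Uneven accrual could move it either way. A report by arm would require the allocation, and exposure would then not be limited to subjects with a Day 14 value in hand. FMD images read after a report date could add further subjects. The documents do not allow either to be counted.

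**The case against.** The strongest reply is that no link in the chain is established. VIII.4 asks for combined data and describes a summarizing report, so subject-level listing is not shown. Providing a report can mean being responsible for its delivery rather than compiling it. VII.E.6 does not say that the PI personally acquires PWV or FMD. VIII.2 says one on-call person is blinded, and he may be the PI. Passages and names were removed, so a compiler or masked assessor may be named where the reader cannot see it. This is also a small single-site pilot with an independent reviewer.

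Much of this stands, and it rules out the reading a reader might infer, that the PI is unblinded or that the trial is not truly double-blind. The documents show neither. But the reply does not close the gap. Only a fully pooled salicylate figure would be harmless, and item b calls the data unblinded. If the person in VIII.2 is the PI, then VIII.2 and VIII.4 conflict and must be reconciled. If he is someone else, his blinding says nothing about PWV or FMD.

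A further fair point is that rerouting the report would not be enough on its own. Because research staff have access to study data (X.4), routine salicylate results could reach the assessors whatever path the report takes. The remedy has to cover that as well.

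**Conclusion.** The point holds as a missing safeguard on the visible text, and it should be fixed. The plan has the PI supply arm-revealing data while the PI and staff obtain the primary outcome, and it states no separation between the two tasks. It is not proof of unblinding.

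The size of any bias is unknown. The 6.6–11.0% (about 2–3 of 30) is an expectation that rests on all four assumptions listed with the calculation. A reader might take it as an upper limit on exposure. It is not one, because it leaves out a report by arm and delayed FMD reading. If values are not listed by subject, this particular route does not arise. Confidence is medium, mainly because of the removed text.

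**What to change.** 1. In VIII.4, have the pathology laboratory, or an existing person who neither acquires nor reads outcomes, send the unblinded salicylate data directly to the independent reviewer. Any outcome summary by arm takes the same route. The PI's own report is limited to pooled data without salicylate.
2. In X.4, restrict access to post-randomization salicylate results in REDCap and the shared files. State that those who acquire or read PWV and FMD, including the PI if he does so, are masked to arm and to these results until their readings are complete.
3. Leave the safety pathway in VIII.2 as written, with results handled by staff who do not measure outcomes where existing staffing allows.
4. State whether the person described as blinded in VIII.2 is the PI and, if so, reconcile that with VIII.4.

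The cost is a few sentences, an access setting and the rerouting of an existing report. Basic chemistries already go to the pathology laboratory (X.4), and salicylate is not among the tests that VII.E.6 (Visit 3) lists under "Extra blood collected for specialized labs performed in PIs lab", so the laboratory route is assumed to need no new assay. The downsides are that the PI sees less interim data and that a compiler must be designated from existing staff in a small team. The reviewer loses nothing.
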